## 4.2. Secondary endpoints

- Occurrence of SAEs from study start (Day 1) up to Day 366.
- Occurrence of RSV-LRTI (AE of specific interest) as from Dose 1 administration up to Day 366.
- Occurrence of RSV-RTI, RSV-LRTI, severe RSV-LRTI (according to standardized case definitions) as from Dose 1 administration up to Day 366.
- Occurrence of SAEs from study start (Day 1) up to study conclusion (Day 731).
- Occurrence of RSV-LRTI (AE of specific interest) as from Dose 1 administration up to study conclusion (Day 731).
- Occurrence of RSV-RTI, RSV-LRTI, severe RSV-LRTI (according to standardized case definitions) as from Dose 1 administration up to study conclusion (Day 731).
- Magnitude of the CMI response to the investigational RSV vaccine, pre-vaccination (Screening), post-Dose 1 (Day 31) and post-Dose 2 (Day 61 and Day 366).
  - CD3+/CD4+ T-cells expressing at least two markers among CD40L, IL-2, TNF- $\alpha$ , and IFN- $\gamma$  upon stimulation with F, N and M2-1 peptide pools.
- Humoral response to the investigational RSV vaccine, pre-vaccination (Screening), post-Dose 1 (Day 31) and post-Dose 2 (Day 61 and Day 366):
  - Neutralizing antibody titers against RSV-A.
  - RSV F antibody concentrations.
- Humoral response to the investigational RSV vaccine, pre-vaccination (Screening), post-Dose 1 (Day 31) and post-Dose 2 (Day 61):
  - Palivizumab-competing antibody concentrations.

### 4.3. Tertiary endpoints

- CMI response profile (Th1, Th2, Th17) to the investigational RSV vaccine, pre-vaccination (Screening), post-Dose 1 (Day 31) and post-Dose 2 (Day 61 and Day 366).
  - CD3+/CD4+ and/or CD3+/CD8+ T-cells expressing at least one or any combination of immune marker(s) among CD40L, 41BB, IL-2, TNF- $\alpha$ , IFN- $\gamma$ , IL-13 and IL-17 upon stimulation with F, N and M2-1 peptide pools.
- Any further exploratory immunology to detect disease-related or vaccine-related immune responses, such as but not limited to:
  - Anti-vector immunity: neutralization. (Analysis for this endpoint will be described in another SAP/AAR).

## 5. ANALYSIS SETS

### 5.1. Definition

#### 5.1.1. Total vaccinated cohort

The total vaccinated cohort (TVC) will include all subjects with at least one study vaccine administration documented.

- A safety analysis based on the TVC will include all vaccinated subjects.
- An immunogenicity analysis based on the TVC will include all vaccinated subjects for whom immunogenicity data are available.

The TVC analysis will be performed per treatment actually administered at Dose 1.

#### 5.1.2. According-to-protocol cohort for analysis of immunogenicity

The ATP cohort for analysis of immunogenicity will be defined by timepoint and will consist of all subjects from the TVC who complied with eligibility criteria, study procedures up to the end of the study and had immunogenicity results in the epoch as described below.

More specifically, the ATP cohort for analysis of immunogenicity up to Visit 9 (Day 61)/at Visit 10 (Day 366) will include all evaluable subjects:

- Who met all eligibility criteria (i.e. no protocol violation linked to the inclusion/exclusion criteria, including age).
- Who received two dose of study vaccine.
- For whom the administration route and site of the vaccine was as according to protocol.

- Who received the vaccine according to protocol procedures.
- Who complied with the vaccination schedule, as specified in Table 5 of the protocol.
- Who did not receive a concomitant medication/product leading to exclusion from an ATP analysis, as described in Section 7.6.2 of the protocol, up to Visit 9 (Day 61)/up to Visit 10 (Day 366).
- Who complied with the timings of the post vaccination blood sampling for immune response evaluation, up to Visit 9 (Day 61) /at Visit 10 (Day 366), as specified in Table 5 of the protocol.
- For whom post-vaccination immunogenicity results are available for at least one assay up to Visit 9 (Day 61) /at Visit 10 (Day 366).

Note that in order to align to ICH and cDISC terminology the Total Vaccinated Cohort and the According to Protocol cohort have been renamed Exposed Set (ES) and Per-Protocol Set (PPS) respectively.

## **5.2. Criteria for eliminating data from Analysis Sets**

Elimination codes are used to identify subjects to be eliminated from analysis. Detail is provided below for each set.

### **5.2.1. Elimination from Exposed Set (ES)**

Code 1030 (Study vaccine not administered at all) and code 900 (invalid informed consent or fraud data) will be used for identifying subjects eliminated from ES

**5.2.2. Elimination from Per-protocol analysis Set (PPS)**

**5.2.2.1. Excluded subjects**

A subject will be excluded from the PPS for analysis of immunogenicity at Day 61 and Day 366 under the following conditions

Code	Condition under which the code is used
900	Invalid informed consent or fraud data ( Subjects receiving a code 900 should not receive any other elimination codes )
1030	Study vaccine not administered at all ( Subjects receiving a code 1030 should not receive any other elimination codes )
1050	Randomization failure
1070\$	Subjects got vaccinated with the correct vaccine but containing a lower volume
1070\$	Administration not according to protocol for reason specified by the investigator, other than side, site and route
1070\$	Site or route of study vaccine administration wrong or unknown
1070\$	Wrong replacement or study vaccine administered (not compatible with the vaccine regimen associated to the treatment number)
1070\$	Administered study vaccine reported as being the correct one but is not compatible with the vaccine regimen associated to the treatment number
1080	Vaccine temperature deviation
1090	Expired vaccine administered
1500\$	Subjects who have received only one dose of vaccination
2010	Protocol violation (inclusion/exclusion criteria)
2080	Subjects did not comply with vaccination schedule (DOSE 1 to DOSE 2 = 23-36 (days))

*\$ Attribution of code to a subject requires CRDL confirmation*

*Please note that all the elimcode has to be checked for the subject under schedule 1.*

**5.2.2.2. Right censored Data**

Data from visit X and subsequent visit will be censored for the PPS analysis under the following conditions. The code **\*\*\*\*.Vx** will be used to identify subjects whose immunogenicity data should be eliminated from a specific visit onwards. Vx will be V9 and V10 with respect to PPS defined up to Visit 9 and Visit 10, respectively.

Code	Decode → Condition under which the code is used
1040*.Vx	Administration of concomitant vaccine(s) forbidden in the protocol → A vaccine not foreseen by the study protocol administered from dose 1 and ending 30 days after the last dose of vaccines administration 
 
• Applicable visits                             
 
– For Day 61 PP, to check from Dose 1 up to Day 61
 
– For Day 366 PP, to check from Dose 1 up to Day 366
 
 
 

1060	Randomization code was broken

*\* Attribution of these elimcodes are responsibility of CRDL following review of individual data listings*

*Please note that all the elimcode has to be checked for the subject under schedule 1 who have received vaccination.*

**5.2.2.3. Visit-specific censored Data**

Data at visit X will be censored for the PPS analysis under the following conditions. The code **\*\*\*\*.Vx** will also be used to identify study withdrawal at visit X. Vx will be V9 and V10 with respect to PPS defined up to Visit 9 and Visit 10, respectively.

Code	Decode → Condition under which the code is used
2040*.Vx	
 
• Administration of any medication forbidden by the protocol →                             
 
– Any investigational or non-registered product (drug or vaccine) other than the study vaccines used during the study period.
 
– Immunosuppressants or other immune-modifying drugs administered chronically (i.e., more than 14 days) during the study period.
 
– Immunoglobulins and/or any blood products administered during the study period
 
– Administration of long-acting immune-modifying drugs during the study period.
 
 
 
• Applicable visits                             
 
– For Day 61 PP (V9), check from Dose 1 up to Day 61 BS
 
– For Day 366 PP (V10), check from Dose 1 up to Day 366 BS
 
 
 

2050*.Vx	
 
• Underlying medical condition forbidden by the protocol
 
• Applicable visits                             
 
– For Day 61 PP, to check from Dose 1 up to Day 61
 
– For Day 366 PP, to check from Dose 1 up to Day 366
 
 
 

2060*.Vx	Concomitant infection related to the vaccine which may influence immune response 
 
• Applicable visits                             
 
– For Day 61 PP (V9), to check from Dose 1 up to Day 61
 
– For Day 366 PP (V10), to check from Dose 1 up to Day 366
 
 
 

2070*.Vx	Concomitant infection not related to the vaccine which may influence immune response 
 
• Applicable visits                             
 
– For Day 61 PP, to check from Dose 1 up to Day 61
 
– For Day 366 PP, to check from Dose 1 up to Day 366
 
 
 

2090.Vx	Subjects did not comply with immunological blood sample schedule 
Applicable visits
 
 
– For Day 61 PP, to check for Dose 1 to Visit 5 BS = 23-36 days and Dose 2 to Visit 9 BS = 28-35 days]
 
– For Day 366 PP, to check for Dose 1 to Visit 10 BS = 335-395 days]
 

Code	Decode → Condition under which the code is used
2100.Vx	Serological results not available post-vaccination → No immunological result at all for the specific blood sample collection timepoint 
 
• Applicable visits                             
 
– For Day 61 PP, check for availability of atleast one assay [CMI (ICS), Neutra, RSV F IgG or PCA result] at Day 31 and Day 61
 
– For Day 366 PP, check for availability of atleast one assay [CMI (ICS), Neutra, RSV F IgG or PCA result] at Day 366
 
 
 

2120 !@ .Vx	Obvious incoherence or abnormality or error in data → Incoherence between CRF and results, wrong sample labelling, Central/internal/external lab deviations; incorrect spinning/processing of sample including processing within the time required by protocol; temperature deviations from range defined in protocol and/or SPM - room temperature/refrigerator/freezer; an assessment was completed, but was not completed according to protocol or SPM. 
 
• Applicable visits                             
 
– For Day 61 PP, check on Day 31 and Day 61 CMI (ICS), Neutra, RSV F IgG or PCA result
 
– For Day 366 PP, check on Day 366 CMI (ICS), Neutra, RSV F IgG or PCA result
 
 
 

\* Attribution of these elimcodes are responsibility of CRDL following review of individual data listings  
 Please note that all the elimcode has to be checked for the subject under schedule 1 who is vaccinated.  
 @this code need confirmation from lab expert of particular test performed  
 ! Attribution of code to a subject requires CRDL confirmation

### 5.3. Important protocol deviation not leading to elimination from per-protocol analysis set

The following important protocol deviations will be reported by groups:

- Forced randomization: In case of supplies shortage for the next assigned vaccine according to the randomization schedule at the clinical site, the randomization system will use the forced randomization procedure in order to continue to enrol and vaccinate subjects. The system moves seamlessly to the next treatment/randomization number for which vaccine supplies are available. The site will not be aware of the forced randomization event.
- Short follow-up: subjects who completed the last study contact before the minimum length of follow-up requirement
- In case unexpected vaccinations at study start were granted due to regulatory recommendation or medical need, the subjects who had such vaccination could be mentioned.

## **6. STATISTICAL ANALYSES**

Note that standard data derivation rule and stat methods are described in annex 1 and will not be repeated below.

### **6.1. Demography**

#### **6.1.1. Analysis of demographics/baseline characteristics planned in the protocol**

The analysis of demographics will be performed on the Exposed Set and on the PPS for analysis of immunogenicity at Day 61 and Day 366 analysis. The analysis of demography will be performed on Exposed Set at Day 731.

Demographic characteristics (age at first vaccination in months, gender, race, country), weight, height or length, and vital signs, and cohort description will be summarized by group using descriptive statistics:

- Frequency tables will be generated for categorical variable such as race.
- Mean, median, standard error and range will be provided for continuous data such as age.

The above analysis will also be done at Day 366 and Day 731 with age at the visit in months.

The weight for age Z score (WAZ) and height or length for age Z score (HAZ) at first vaccination, Day 366 and Day 731 will be calculated on ES. The distribution of subjects will be tabulated as a whole and per group.

Withdrawal status will be summarized by group using descriptive statistics.

- The numbers of withdrawn subjects will be tabulated according to the reason for withdrawal on ES.
- The number of subjects enrolled into the study as well as the number of subjects excluded from PPS analyses will be tabulated.

### **6.2. Immunogenicity**

#### **6.2.1. Analysis of immunogenicity planned in the protocol**

The primary analysis will be performed on the PPS for analysis of immunogenicity and a complementary analysis will be performed on Exposed Set. All the immune analysis is within group only.

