1. INTRODUCTION

1.1. Background

1.1.1. RSV disease burden

Respiratory syncytial virus (RSV) is a ribonucleic acid virus of which two antigenically distinct subgroups exist, referred to as RSV-A and RSV-B [Borchers, 2013]. RSV is a highly contagious human pathogen that causes respiratory tract infections (RTI) in people of all ages.

During the first year of life, 50-70% of infants are infected with RSV and essentially all children have had an RSV infection by their second birthday. The risk for severe RSV-associated lower respiratory tract infections (LRTI) is highest in infants below 6 months of age and is a leading cause for hospitalization. It is estimated that on average 31 per 1000 children below 6 months of age are hospitalized for RSV-associated severe LRTI [Boyce, 2000; Deshpande, 2003; Hall, 2009; Holman, 2004; Iwane, 2004; Paramore, 2004; Vicente, 2003]. 50-70% of these hospitalized children do not have additional risk factors like preterm birth or cardiopulmonary disease [Boyce, 2000; García, 2010; Hall, 2009; Rietveld, 2004]. For human immunodeficiency virus (HIV)-infected children, the incidence rate of hospitalization for RSV-associated LRTI was reported to be 2.5- to 5-fold greater than in HIV-uninfected children [Cohen, 2015; Madhi, 2006]. Although RSV hospitalization rates substantially decrease after 6 months of age, a considerable number of RSV infections in children of 6-15 months of age, still lead to bronchiolitis or (broncho)pneumonia requiring medical attention [Fisher, 1997].

Previous infection with RSV does not prevent subsequent infections. Therefore, re-infection with RSV occurs throughout an individual's lifetime and is common in all age groups [Simoes, 1999; Krilov, 2011]. These re-infections generally go undiagnosed because they usually present as common acute upper respiratory tract infections. In more vulnerable persons (e.g. immunocompromized subjects or elderly), re-infections can however also lead to severe disease [Graham, 2011].

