1.2.6. Rationale for the use of placebo

The placebo group is included as a control for the reactogenicity, the safety and the immunogenicity assessments.

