#### **3.2. Secondary objectives**

- To evaluate the safety of two IM doses of three dose levels of the RSV investigational vaccine when administered according to a 0, 1-month schedule from study start (Day 1) up to study conclusion (Day 731) in RSV-seropositive infants aged 12 to 23 months
- To evaluate the occurrence of RSV respiratory tract infections in RSV-seropositive infants from Visit 1 (Day 1, after Dose 1) up to study conclusion (Day 731)
- To evaluate the magnitude of the CMI induced by two IM doses of three dose levels of the RSV investigational vaccine when administered according to a 0, 1-month schedule, up to Day 366 in RSV-seropositive infants aged 12 to 23 months.
- To evaluate the humoral immunogenicity induced by two IM doses of three dose levels of the RSV investigational vaccine when administered according to a 0, 1-month schedule, up to Day 366 in RSV-seropositive infants aged 12 to 23 months

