### 6.2.1.1. CMI analysis

The analysis will be performed on each group separately, pooled placebo group and pooled RSV group. All the CMI analysis will be performed for each peptide pool (F, N, M2-1) separately and taking all the peptide pool together for subjects who has data available for the three peptide pools.

With respect to secondary objectives, the following parameters will be summarized by group using descriptive statistics (N, geometric mean [GM], minimum [min], 1st quartile [Q1], median, third quartile [Q3], maximum [max]), at each timepoint during which blood samples are collected for CMI in investigational sites with a laboratory in proximity capable to perform WBS necessary for the CMI assay:

- Frequency of CD4+ T-cells expressing at least two markers among CD40L, IL-2, TNF- $\alpha$ , and IFN- $\gamma$  upon stimulation with F, N and M2-1.
- Box plot with individual data for CD4+ T-cells expressing at least two markers among CD40L, IL-2, TNF- $\alpha$ , and IFN- $\gamma$  upon stimulation with F, N and M2-1 and combined peptide pool will be presented.

With respect to tertiary objectives, the cellular immune response will be further characterized using descriptive analysis of the frequency of CD8+ T-cells and CD4+ T-helper cell profile (Th1, Th2, Th17) expressing at least one or any combination of marker(s) among CD40L, 41BB, IL-2, TNF- $\alpha$ , IFN- $\gamma$ , IL-13, and IL-17.

The following parameters will be summarized by group using description statistics (N, GM, min, Q1, median, Q3, max), at each timepoint during which blood samples are collected for CMI:

- Frequency of CD4+ and CD8+ T-cells expressing at least one or any combination of immune marker(s) among CD40L, 41BB, IL-2, TNF- $\alpha$ , IFN- $\gamma$ , IL-13 and IL-17 upon stimulation with F, N and M2-1 peptide pools.
- Tabular presentation of T-helper cell 'Th1' profile - Frequency of CD4+ T-cells expressing at least IFN- $\gamma$  but no IL-13 upon stimulation with F, N and M2-1 peptide pools.
- Tabular presentation of T-helper cell 'Th2' profile: Frequency of CD4+ T-cells expressing at least IL-13 but no IFN- $\gamma$  upon stimulation with F, N and M2-1 peptide pools.
- Tabular presentation of T-helper cell 'Th17' profile - Frequency of CD4+ T-cell expressing atleast IL17 upon stimulation with F, N and M2-1 peptide pools.
- Calculation of 'Th2/Th1 ratio' = Frequency of Th2 T-cells / frequency of Th1 T-cells.

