#### **6.2.1.2. Humoral immune response**

For each group, at each timepoint that blood samples are collected for humoral immune response against the investigational RSV vaccine (neutralizing antibody titers against RSV-A, RSV F antibody concentrations, and palivizumab-competing antibody concentrations):

- GMTs/GMCs will be tabulated with 95% CI and represented graphically.
- Percentage of subjects above the seropositivity threshold will be tabulated with exact 95% CI.
- Antibody titers/concentrations will be displayed using reverse cumulative curves.
- The distributions of neutralizing antibody titers/concentrations will be tabulated (< 128, 128-256, > 256-512, > 512-1024, > 1024-2048, > 2048-4096, > 4096)
- Percentage of responders in terms of RSV-A neutralizing antibody titers will be tabulated with exact 95% CI.
- Individual post-vaccination versus pre-vaccination results will be plotted using scatter plots. Results of the Placebo groups will be used as a reference.
- Geometric mean of ratios of antibody titers/concentrations at each post-vaccination timepoint over pre-vaccination will be tabulated with 95% CI.
- Distribution of the fold increase of the neutralizing antibody titers will be tabulated by pre-vaccination titer category (percentage of subjects with a fold increase equal to or above 1, 2, 2.5, 3, 4, 6, 8, 10, 11 and 12 by pre-vaccination titre category: (< 128, 128-256, > 256-512, > 512-1024, > 1024-2048, > 2048-4096, > 4096, and by cumulative category: <128,  $\geq$ 128,  $\geq$ 256,  $\geq$ 512,  $\geq$ 1024,  $\geq$ 2048,  $\geq$ 4096.).
- The kinetics of individual antibody titer/antibody concentration results will be plotted as a function of time for subjects with results available at all timepoints.

If available, any further exploratory immunology results (including, but not limited to anti-vector immunity) will be reported by group and timepoint using descriptive summary statistics will be described separately in Additional analysis request (AAR).

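### No vaccine-versus-placebo immunogenicity estimate with a confidence interval is pre-specified, although placebo is the stated immunogenicity control

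*SAP*

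**What the plan says.** The SAP's secondary objective (3.2) is "To evaluate the humoral immunogenicity induced by two IM doses of three dose levels" of the vaccine. Protocol 1.2.6 gives the reason for the control arm: "The placebo group is included as a control for the reactogenicity, the safety and the immunogenicity assessments".

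The analysis rule in SAP 6.2.1 is: "All the immune analysis is within group only". Protocol 11.9 has the same scope, since its only analysis subsection (11.9.1) is a within-groups assessment.

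The main measure of change in SAP 6.2.1.2 is computed inside each arm: "Geometric mean of ratios of antibody titers/concentrations at each post-vaccination timepoint over pre-vaccination will be tabulated with 95% CI". Placebo enters that section by name through the scatter plots: "Results of the Placebo groups will be used as a reference". For cell-mediated immunity, SAP 6.2.1.1 says: "The analysis will be performed on each group separately, pooled placebo group and pooled RSV group".

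Safety is handled differently. SAP 6.4.1.2 plans step-matched differences (RSV-Ld minus Placebo-Ld, and likewise for Md and Hd) with 95% CIs.

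**The concern.** A response induced by the vaccine is a causal target, and a within-arm post/pre ratio does not estimate it. That ratio mixes the vaccine effect with whatever else moved the titre. The protocol expects other things to move it. Section 1.1.1 says "Previous infection with RSV does not prevent subsequent infections" and describes re-infection as common at all ages. The infants are seropositive, 12 to 23 months old at entry, and sampled for neutralising and RSV F antibody until Day 366, so both boosting by infection and waning are possible.

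The staggered design adds to this. The three dose levels enrol one after another, so their follow-up may meet different RSV exposure. Within-arm rises will naturally be read across doses. The concurrent placebo group in each step is the protection against that, and no planned estimate uses it.

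At stake is the reading of a secondary objective. Any statement that a dose raised titres by a given factor would carry an interval for total change in that arm, not for the vaccine effect.

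**Working it through.** **1. What each planned quantity estimates.** On the log10 scale, with V the vaccine effect and B the background change in that step:

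- RSV arm, post/pre: V + B
- placebo arm, post/pre: B
- difference: V

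The SAP reports the first two, each with its own CI. It does not report the third.

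**2. What reading two intervals by eye costs.** With equal half-widths h, requiring the two CIs not to overlap needs a separation of 2h. The CI for the difference has half-width √2·h ≈ 1.41h. The eye test therefore asks for 2/1.41 ≈ 1.41 times the necessary separation, and it gives no estimate of V.

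**3. The responder rule.** SAP 11.3.4 counts any post/pre ratio of at least 1 as a response when the pre-vaccination titre exceeds 1024. If the log ratio is symmetric about zero (no true change, only noise), P(ratio ≥ 1) = 0.5. Regression to the mean in infants selected for a high baseline would lower this, and natural infection would raise it. A within-arm responder rate therefore has no fixed null value, and placebo has to supply it.

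**4. The plan's own precision figure.** Neither document states precision or power for immunogenicity. Protocol 11.4 gives only a safety figure: a maximum exact 95% CI width of about 50% with 16 vaccinees. This reproduces as 50.7% (at 8 of 16). It fixes the group size and is not disputed.

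**5. Precision of the missing contrast.**

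Inputs from the documents:
- 1:1 allocation, 8 to 16 per group in Steps 1 and 2, 16 per group in Step 3 (Protocol 6.2.2.2.1).

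Inputs assumed, because the documents give neither:
- SD of log10 titre 0.3 to 0.5.
- Pre/post correlation ρ 0.5 to 0.8.

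Formula for ANCOVA with baseline: CI factor = 10^[t(2n−3) × SD × √(1−ρ²) × √(2/n)].

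- 16 v 16, best case: 2.045 × 0.3 × 0.600 × 0.354 = 0.130, factor 1.35
- 16 v 16, worst case: 2.045 × 0.5 × 0.866 × 0.354 = 0.313, factor 2.06
- 8 v 8, best case: 2.160 × 0.3 × 0.600 × 0.500 = 0.194, factor 1.57
- 8 v 8, worst case: 2.160 × 0.5 × 0.866 × 0.500 = 0.468, factor 2.94
- Pooled, ρ 0.5, SD 0.3 to 0.5: factor 1.35 to 1.65 at 32 v 32, and 1.27 to 1.50 at 48 v 48

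**6. Is that precision useful?** The only effect size in the documents is the adult study's rise of about 2.4-fold from baseline (Protocol 1.1.6). As a yardstick only, an observed RSV/placebo ratio of 2.4 would have these lower limits:

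- 16 v 16: 2.4/2.06 = 1.17 to 2.4/1.35 = 1.78
- 8 v 8: 2.4/2.94 = 0.82 to 2.4/1.57 = 1.53

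The contrast is informative at 16 per group and marginal at 8.

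**7. Why adjust for baseline.** Relative to comparing post-vaccination titres alone, the SE is multiplied by √(1−ρ²), which is 0.87 to 0.60. Relative to comparing post/pre changes, it is multiplied by √[(1+ρ)/2], which is 0.87 to 0.95. This supports the choice of model. It does not measure the gap, which is the absence of any contrast.

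**The case against.** The strongest reply is that the study is descriptive by design. Protocol 11.4 disclaims any hypothesis-driven sample size, SAP Section 7 calls all analyses descriptive, groups may hold only about 8 infants, and the SAP follows Protocol 11.9 faithfully. All of this is true. It explains why no test is planned. It does not explain why an exploratory estimate with a CI is withheld here and given for safety in 6.4.1.2.

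The second reply is that placebo and baseline are already used, and this also stands. Templates 37 to 41 list all three placebo groups, so GMTs, responder rates and post/pre ratios are produced for them. Figure 4 plots vaccine results with control results, and Figure 3 compares the groups for each assay and time point. Baseline enters the post/pre ratios, the fold-increase tables and the responder rule. A reader might infer from 6.2.1 that the control and baseline go unused, or that natural boosting and waning cannot be told apart from the vaccine effect at all. The documents do not support either inference, because a placebo fold-change with its CI beside the vaccine fold-change does show background change.

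The third reply is that infection is handled: codes 2060 and 2070 (SAP 5.2.2.3) censor per-protocol data for concomitant infections that may influence the immune response. This is partial cover. The codes act after randomisation, depend on detection and on review by the sponsor's clinical lead, and do nothing about waning. They also do not apply to the Exposed Set, whose eliminations (5.2.1) are limited to codes 1030 and 900.

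**Conclusion.** The concern holds in a limited form. No between-group immunogenicity ratio or difference, no CI for one and no baseline-adjusted model is pre-specified, although placebo is the declared immunogenicity control and the objective is causal. The planned summaries allow an informal comparison but leave background change inside every reported effect estimate.

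This is a worthwhile, inexpensive improvement and does not invalidate the plan. The finding rests on the text and needs no numerical assumption. Only the precision does: with SD 0.3 to 0.5 log10 and correlation 0.5 to 0.8, the CI factor is about ×/÷1.35 to 2.1 at 16 versus 16 and ×/÷1.6 to 2.9 at 8 versus 8. That is exploratory precision, and Steps 1 and 2 could be weak on their own if they stop at 8 per group.

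**What to change.** - **SAP 6.2.1:** replace the within-group-only sentence with a statement that immune analyses are within group, plus the exploratory between-group comparisons in 6.2.1.2.
- **SAP 6.2.1.2:** add an exploratory ANCOVA on log10 titre or concentration, with group and log10 pre-vaccination value as terms. Run it for RSV-A neutralising and RSV F antibody at Days 31, 61 and 366. Run it for palivizumab-competing antibody at Days 31 and 61 only, because that assay has no Day 366 endpoint (SAP 4.2; Protocol Table 12).
- **Comparisons:** report the baseline-adjusted geometric mean ratio with 95% CI for RSV-Ld v Placebo-Ld, RSV-Md v Placebo-Md and RSV-Hd v Placebo-Hd, the pairs already used in 6.4.1.2. Add pooled RSV v pooled placebo, adjusted for step so that calendar time and RSV exposure are not mixed in.
- **SAP Section 7:** extend the wording on comparative analyses, now limited to safety and reactogenicity, to immunogenicity. The existing caution on small groups and multiplicity then applies.
- **SAP Section 9:** list the addition as a change from the protocol, and justify it in the study report as Protocol 11.12 requires.

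Cost: no new samples or visits. There are 3 + 3 + 2 = 8 assay-time points, so 8 × 3 = 24 step-matched contrasts and 8 pooled ones. None is adjusted for multiplicity, and all should be labelled exploratory. The change leaves the cell-mediated summaries as they are; those samples come only from sites near a capable laboratory.
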